6.5.1.4 Categorical longitudinal Outcomes

Will utilise the same methodology as the continuous models but using an appropriate logit link in a generalised linear model. Odds ratios (and 95% confidence intervals) will be used to illustrate comparisons between treatment groups.

6.5.2 Secondary Analyses of Secondary Outcomes

The count outcomes (number of hospital readmissions and number of moderate exacerbations over 48 weeks) will be analysed in the per protocol (PP) population. Analysis methods will mirror those described in the primary analysis of secondary outcomes, except the offset will be log time on trial treatment (4 weeks after the last dose, capped by death).

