3.2 Secondary Outcomes

3.2.1 Definition and Derivation of Secondary Outcomes

Exacerbations and Healthcare Utilisation

- Time from randomisation to next hospital readmission or death due to a respiratory cause

The time from randomisation to next hospital readmission or death (due to a respiratory cause) is defined as a time to event outcome measured in days. The date of randomisation as well as the date of readmission or death due to respiratory causes (whichever occurs first) will be used to calculate time to event. For participants not experiencing an event the time will be calculated from randomisation until last known follow-up assessment event-free. A variable to indicate event (with a value of 1) or no event (with a value of 0) will be derived. Details of the primary outcome analysis are included in section 5.5.

- Total number of hospital readmissions all cause up to 48 weeks

The total number of hospital readmissions (all cause) is defined as a count outcome. The number of hospital readmissions (all cause) in total during the 48 (truncated follow-up

minimum 24) weeks corresponding to each participant will be calculated. Where no hospital admission have occurred a value of zero will be derived.

- Total number of moderate exacerbations up to 48 weeks

The total number of moderate exacerbations is defined as a count outcome. The severity of a COPD exacerbation will be deemed as “Moderate” if the participant required treatment with steroids or antibiotics and was not hospitalised (Oba, Y. et al, 2017).

The number of moderate exacerbations each participant had over the course of 48 (truncated follow-up minimum 24) weeks will be calculated.

- Time from randomisation to treatment failure (defined as the composite of three endpoints: 1. treatment intensification with systemic corticosteroids and/or antibiotics for respiratory reasons; 2. step-up in hospital care for respiratory reasons including transfer to the intensive care unit or readmission; or 3. all-cause mortality)

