4.1.2 Minor deviations

Participants visit/assessment not performed as per protocol

4.2 *Intention-to-treat Population*

The primary analysis for each efficacy outcome will be by ‘intention to treat’ analysis; all the participants randomised into the trial (regardless of whether they received trial drug) will be analysed in their allocated group. Outcome data obtained from all participants will be included in the data analysis.

4.3 *Modified intention-to-treat population*

The modified intention-to-treat will be comprised all the participants randomised to the trial (regardless of whether they received trial drug), analysed in their allocated group, where data is available. Therefore, participants with missing outcome data will be excluded from the analysis (i.e complete case analysis). No imputation will be carried out for the missing data.

4.4 *Per-protocol Population*

The per protocol population will contain all participants randomised who do not reach any of the listed definitions for major protocol deviations. Individuals without a major deviation will be included in the per-protocol population whilst on trial treatment, this is considered to be 4 weeks after the last dose. If a participant dies before ending trial treatment, time is capped by death date.

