6.4.2 Secondary Analyses of Primary Outcomes

The secondary analysis of the primary outcome will take place on a subset of participants defined by the per-protocol population with individuals being censored at the earliest of end of their trial treatment (4 weeks after last dose) or last follow-up. The analysis will otherwise match the approach described above for the primary analysis.

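### SAP 6.5.2 limits the offset of the per-protocol count analysis to time on treatment but does not limit the events to the same window, and it leaves out the cap at last follow-up that 6.4.2 uses

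*SAP*

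**What the plan says.** - **SAP 6.5.2** analyses the "number of hospital readmissions and number of moderate exacerbations over 48 weeks" in the per-protocol population. Methods follow the primary analysis of these outcomes, "except the offset will be log time on trial treatment (4 weeks after the last dose, capped by death"). That is the only exception it states.
- **SAP 3.2.1** holds the only derivation of the counts. For readmissions it begins "The number of hospital readmissions (all cause) in total during the 48 (truncated follow-up" and continues with a 24-week minimum for truncated participants. Moderate exacerbations are counted over the same span.
- **SAP 6.5.1.3**, the analysis being mirrored, uses log time on study as the offset (capped at 49 weeks) and analyses all available observed data without deletion.
- **SAP 4.4** says that people without a major deviation are "included in the per-protocol population whilst on trial treatment, this is considered to be 4 weeks after the last dose", with time capped at death.
- **SAP 6.4.2**, the per-protocol analysis of the primary outcome, writes its window out in full: "individuals being censored at the earliest of end of their trial treatment (4 weeks after last dose) or last follow-up".
- **Protocol 7.8** asks participants who stop treatment to agree to further data collection, at least on admissions and deaths, to 48 weeks. **Protocol 7.11** follows those lost to follow-up through hospital records to 48 weeks (or to their planned final visit if truncated).

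**The concern.** A rate needs its events and its time to come from the same interval. Section 6.5.2 shortens the time and is silent on the events. A programmer who follows 6.5.2 and 3.2.1 would divide a 48-week count by on-treatment time. One who starts from 4.4 would drop events later than 4 weeks after the last dose. The two datasets differ for everyone who stops early and is still followed, and the SAP does not say which to build. If that is settled after unblinding, it becomes an analyst's choice about which events count.

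Under the literal reading the estimate is not an on-treatment rate. It is too high in each arm, and the rate ratio moves if stopping is unequal. The arm with more stopping looks worse.

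The missing cap at last follow-up is a smaller fault in the opposite direction: it adds time in which events cannot be observed and so lowers the rate.

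**Working it through.** **No figure to reproduce.** The documents give no event rate, stopping rate or power for this analysis. All stopping rates below are assumptions.

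**Step 1. Who is affected under the literal reading.**

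| Participant | Later events counted without matching time? |
|---|---|
| Dies | No: time is capped at death and there are no later events |
| Withdraws consent | No: no later data (but see step 5) |
| Stopped for non-compliance | No: major deviation under SAP 4.1.1, so outside the set |
| Planned truncated follow-up, completes dosing | No: final visit is 4 weeks after last dose, so the windows match |
| Stops for another reason (for example adverse event, intolerance, investigator decision) and stays in follow-up | **Yes** |

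The last row is a real group. For missed doses, SAP 4.1.1 makes only discontinuation for non-compliance a major deviation.

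**Step 2. Individual rates.** At a constant event rate, with last dose at week L, the overstatement is 48/(L + 4):

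- L = 0: 12
- L = 8: 4
- L = 20: 2
- L = 36: 1.2
- L = 44: 1.0

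Example: last dose at week 8, three readmissions in 48 weeks, one of them by week 12. Literal: 3/12 × 52 = 13.0 per year. Matched: 1/12 × 52 = 4.3 per year.

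**Step 3. Pooled rates.** Let p be the share who stop early and are followed to 48 weeks. Assume their last dose is uniform over weeks 0, 4, ..., 40, so its mean is 20 and mean on-treatment time is 24 weeks. The average offset time is 48(1 − p) + 24p = 48 − 24p, and the overstatement is 48/(48 − 24p):

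- p = 10%: 48/45.6 = 1.05
- p = 20%: 48/43.2 = 1.11
- p = 30%: 48/40.8 = 1.18
- p = 40%: 48/38.4 = 1.25

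**Step 4. Rate ratio when the true value is 1.** The event rate cancels.

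- Equal stopping in both arms: 1.00.
- 15% placebo v 30% mepolizumab: (48/40.8)/(48/44.4) = 44.4/40.8 = 1.09. Reversed: 40.8/44.4 = 0.92.
- Negative binomial model with the same stopping pattern, dispersion 0.5 and −ln(0.35)/48 × 52 = 1.14 events per year (the constant hazard implied by the plan's 65% at 48 weeks): about 1.11 and 0.90. It is further from 1 because the model gives short exposures relatively more weight than pooling does.
- If at least 20 weeks of dosing is required (last dose uniform over weeks 20 to 40, mean on-treatment time 34 weeks, average 48 − 14p): 45.9/43.8 = 1.05 and 43.8/45.9 = 0.95. The negative binomial model gives about 1.05 and 0.96.
- A harsher case: all stoppers have 12 weeks on treatment, with 1.0 to 1.5 events per 48 weeks and dispersion 0.7. The simulated ratio is 1.22 to 1.23 for 15% v 30%, and 0.81 to 0.83 for 30% v 15%.
- With events and offset on the same window, that simulation (113 per arm, 300 runs per scenario) returns 0.98 to 1.01 across its stopping patterns.

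**Step 5. No cap at last follow-up.** Suppose a share w withdraws just after a dose, and each adds the full 4 unobservable weeks. With the step 3 timing, the spurious share of person-time is 4w/(48 − 24w): 0.2/46.8 = 0.4% for w = 5%, and 0.8/43.2 = 1.9% for w = 20%.

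**The case against.** The strongest reply is that SAP 4.4 already settles the matter. It defines the per-protocol population by time as well as by person, 6.5.2 invokes that population, and the offset repeats the same window. On that reading events after the window fall outside the set, and the 48 weeks in 6.5.2 is only the name of the outcome. As evidence of intent this stands, so a reader should not infer that the SAP deliberately specifies mismatched windows. It does not remove the gap. Section 4.4 does not redefine the count variable, 6.5.2 names the offset as its one exception, and for the primary outcome the authors did not rely on 4.4 but wrote the censoring rule out.

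A reader might also infer that anyone who stops early gets an inflated rate. The table in step 1 shows that this is too broad. The effect on moderate exacerbations is less certain than on readmissions: the minimum data after stopping are admissions and deaths, and hospital records may miss events that are by definition not hospitalised.

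The size depends on assumed stopping rates, on following every such stopper to 48 weeks, and on ignoring truncation and death. Protocol 10.3.3 and 10.7 also require at least 24 weeks of treatment for these per-protocol analyses, a rule that SAP 4.4 lacks. If it applies (read as last dose at week 20 plus 4 weeks), the week-8 example drops out and the smaller figures in step 4 are the relevant ones. That difference between the documents must be reconciled in its own right.

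**Conclusion.** The point holds as a conflict between sections and an incomplete definition. SAP 6.5.2 with 3.2.1 gives a 48-week count over on-treatment time, while 4.4 implies an on-treatment count. The literal reading overstates rates only for participants who stop for reasons other than non-compliance, death or consent withdrawal and remain in follow-up. It biases the rate ratio only if such stopping differs by arm. At an assumed 15% v 30% the bias is roughly 10% either way, or about 5% if at least 20 weeks of dosing is required. The documents do not show that stopping will differ, so bias is a possibility and not a finding.

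The missing cap at last follow-up holds under either reading, because neither 6.5.2 nor 4.4 supplies it. It is worth about 0.4% to 1.9% of person-time if 5% to 20% withdraw just after a dose.

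Both faults are confined to a supportive analysis of secondary outcomes. The main count analysis (SAP 6.5.1.3) uses time on study and the primary outcome is analysed separately, so neither is affected.

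**What to change.** Add to SAP 6.5.2, with a cross-reference from 3.2.1:

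> For the per-protocol count analyses, only events from randomisation to the earliest of 4 weeks after last dose, last follow-up and death are counted, and the offset is the log of that same interval.

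This agrees with 4.4, brings the end of the window into line with 6.4.2 and also states where the interval starts, which 6.5.2 does not. The cost is one sentence and a date filter in the count derivation, made before database lock. The downside is slightly fewer events in a supportive analysis.

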6.5.3 Sensitivity Analyses

The primary analyses for all none time event outcomes (i.e continuous, binary and count outcomes) will consider any missing data to be missing at random (MAR) and complete case analysis carried out. However, if comparison of patterns of missingness and descriptive differences between treatment arms indicate this assumption is not valid, additional sensitivity analyses may be carried out and methods of imputation will be included in detail in the statistical analysis plan.

To ensure the reliability of the analysis of key secondary outcome measures, we will conduct a sensitivity analysis under various scenarios. This will involve evaluating the secondary outcomes; number of readmissions, number of exacerbations, and SGRQ (assessed for three sub-domains and the total score), to thoroughly assess the robustness of our results.

Individuals will be considered to have had some missing data for the two count variables if they have less than 47 weeks (48 weeks – 7day window) follow-up with the exception of those with planned truncated follow-up.

In the first approach, regardless of whether missingness is assumed to be random or non-random, we will perform the outlined statistical procedures. Additionally, we will provide descriptive characteristics of the missing group compared to the non-missing group, exploring potential similarities or dissimilarities between them. This comprehensive approach allows for a thorough examination of the impact of missing data on our study outcomes.

In the second approach, we are aware that throughout the trial, some participants may leave the study due to a high number of exacerbations or death before reaching their 48-week follow-up. This leads to missing data that is not at random, rendering

standard imputation methods inappropriate. Therefore, the data for key secondary outcomes for these participants will be analysed in the following way:

Pattern Mixture Model:

Robustness of the results will be assessed within the pattern mixture model. A pattern mixture model is a type of statistical model used to analyse data with missing values, especially when the missingness is not at random (MNAR).

This method is a 2-stage procedure where the 1st stage involves the use of multiple imputation to impute all missing values assuming data are “missing at random”.

The 2nd stage involves changing the imputed values for those participants from the time that they leave the study due to a high number of exacerbations or death before reaching their 48-week follow-up.

For the 2nd stage, the following approach will be used:

- 1) Changing all imputed values for these participants to their last observation of the key secondary outcomes before they exit the study due to exacerbations or death. ^a
- 2) Adjusting all imputed values for participants who exit the study due to exacerbations or death to a constant value (i.e. the mean of the outcome variable in the control group). ^b

^a For the count variables, observed data will be carried forward by imputing the number expected in 48 weeks to be at the same rate as for the observed period rounded to the nearest whole number.

^b For the count variables, observed data will included for the time period observed with the number for the remaining time period being imputed at the rate observed in the control group (using all observed control data weighed for the time observed) rounded to the nearest whole number for that time period.

Note: For Stage 1, all missing data will be imputed using multiple imputation with chained equations in Stata 18 (or above). Stata’s “MI” command will be used to carry out this analysis and No data will be imputed past point of death.

Overall, 50 imputations will be generated for any missing data for the key secondary outcome and all stratification variables, treatment arm, and baseline value will be used to aid the multiple imputation procedure. Imputed results will be combined using Rubin’s rule which in Stata is the “mi estimate” command.

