MA	Marketing Authorisation
MACE	Major Adverse Cardiac Events
MedDRA	Medical Dictionary for Regulatory Authorities
MHRA	Medicines and Healthcare products Regulatory Agency
MS	Member State
NHS R&D	National Health Service Research & Development
NIMP	Non-Investigational Medicinal Product
NYHA	New York Heart Association
PCR	polymerase chain reaction
PI	Principal Investigator
PIC	Participant Identification Centre

PIS	Participant Information Sheet
PPI	Public and Patient Involvement
QA	Quality Assurance
QC	Quality Control
QP	Qualified Person
RCT	Randomised Control Trial
REC	Research Ethics Committee
RNA	ribonucleic acid
SAE	Serious Adverse Event
SAR	Serious Adverse Reaction
SC	Subcutaneous
SDV	Source Data Verification
SGRQ	St. George's Respiratory Questionnaire
SmPC	Summary of Product Characteristics
SOP	Standard Operating Procedure
SPPB	Short Physical Performance Battery
SSI	Site Specific Information
SUSAR	Suspected Unexpected Serious Adverse Reaction
TMF	Trial Master File
TMG	Trial Management Group
Trop I	Troponin I
TSC	Trial Steering Committee
VOC	Breath Volatile Organic Compounds
WOCBP	Women of child-bearing potential

iii. TRIAL SUMMARY

Trial Title	A Randomised Controlled Trial of Mepolizumab Initiated Following Admission to Hospital for a Severe Exacerbation of Eosinophilic COPD
Short title	Mepolizumab for COPD Hospital Eosinophilic admissions Pragmatic trial
Trial acronym	COPD-HELP
Chief Investigator	[name]
Principal Investigator	[name]
Clinical Phase	Phase IIb
Trial Design	Interventional double-blinded, placebo, parallel, randomised controlled trial
Trial Participants	Patients admitted to hospital with an exacerbation of eosinophilic COPD
Planned Sample Size	238
Treatment duration	Mepolizumab 100mg will be administered subcutaneously once every 4 weeks up to 44 Weeks, minimum 20 weeks
Follow up duration	Up to 48 weeks, minimum 24 weeks
Planned Trial Period	4 years
Investigational Medicinal Product(s)	Mepolizumab
Formulation, Dose, Route of Administration	100mg powder for solution or solution in pre-filled syringe for injection. One subcutaneous injection every 4 weeks. Humanised monoclonal antibody which inhibits the bioactivity of the cytokine interleukin-5 (IL-5)

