7.11 End of trial

This trial will end when the specified number of participants have been recruited, all participants have completed their last follow up visit, data validation has taken place and the database is locked and statistical analysis complete.

Data reported in the final report to REC and MHRA within 12 months of the End of Trial will include the primary and secondary outcomes (see sections 3.3.1 and 3.3.2).

Participants who become lost to Follow Up will be followed-up via their hospital records until 48 weeks to collect information on the number of exacerbations, number of hospitalisations and death. Those consented to truncated follow-up (consented to study from July 2023 onward) will be followed-up via their hospital records until their Final Follow-up visit which will occur 4 weeks \pm 7 days from what would have been their final dosing visit (based on when they are consented to the trial).

The trial will be stopped prematurely if:

- Mandated by the Ethics Committee or the Sponsor
- Mandated by the Medicines and Healthcare products Regulatory Agency (MHRA)
- Following recommendations from the Data Safety Monitoring Committee (DSMC) or otherwise the Trial Steering Committee (TSC) determine the trial should stop
- Funding for the trial ceases

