1.1.3 Subgroup Objectives

To evaluate if the efficacy, in terms of the primary outcome, is different between grouped baseline stratification factors of 1) MRC dyspnoea score (≤ 3 , > 3) and 2) past hospitalisation in the previous 12 months (0 , ≥ 1) and WHO clinical progression score at baseline (4, 5, 6).

2 Study Design

This will be a single-centre, double-blinded, randomised, placebo-controlled trial comparing mepolizumab 100mg versus placebo in patients with eosinophilic COPD, started during their index admission to hospital. 238 participants will be recruited over a 3-year period.

Participants will be dosed every 4 weeks for 48 weeks and be followed up for 12 months with the exception of those randomised during the truncated follow-up period.

2.1 *Truncated follow-up*

Patients randomised from July 2023 to December 2023 will be consented to a truncated follow-up model, whereby the timing of the last patient last visit will remain on the same timeline as originally planned; this will result in participants consented in July to have up to the 44-week follow-up, those in August will have up to the 40-week follow-up, and so on. Patients will be dosed for a minimum of 20 weeks, with secondary outcomes measured as per original timelines (baseline, 4 weeks, 8 weeks, etc.) however final outcome measures normally measured at 48 weeks will occur at 4 weeks \pm 7 days post final dosing visit.

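### The missing-data flag for the two count outcomes in SAP 6.5.3 exempts every truncated-follow-up participant, including those who withdraw well before their planned end

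*SAP*

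**What the plan says.** SAP 6.5.3 plans a sensitivity analysis of "number of readmissions, number of exacerbations, and SGRQ (assessed for three sub-domains and the total score". For the counts it defines missingness by length of follow-up: "Individuals will be considered to have had some missing data for the two count variables". The condition for this is stated as "if they have less than 47 weeks (48 weeks – 7day window) follow-up". The exemption closes the same sentence, which ends "follow-up with the exception of those with planned truncated follow-up". No other threshold is given for the exempt participants, and none appears elsewhere in the SAP.

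The flag has two uses in that section. Participants with and without missing data are compared descriptively. A pattern mixture model then runs in two stages: multiple imputation of missing values under missing at random, followed by changes to the imputed values of participants who left because of many exacerbations or death. Footnote a sets the count target at 48 weeks. Footnote b fills the remaining period without naming an end. The section also rules out imputing beyond death.

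Planned follow-up for the truncated cohort can be worked out. SAP 2.1 and Protocol 4.1 have "participants consented in July to have up to the 44-week follow-up, those in August will have up to the 40-week follow-up, and so on", for randomisation from July to December 2023. The Protocol trial summary gives the range as "Up to 48 weeks, minimum 24 weeks". Protocol 7.11 fixes the end of record follow-up for truncated participants who are lost by reference to "what would have been their final dosing visit (based on when they are consented to the trial").

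**The concern.** The purpose of the exemption is presumably to avoid calling follow-up missing when it is short by design. As worded it goes further and covers a truncated participant whose follow-up is short because they left. Having less than 47 weeks tells the analyst nothing in this cohort, so the rule needs a different threshold there, and the SAP supplies none.

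Two results are at stake. The comparison of missing with non-missing participants would place truncated early leavers on the non-missing side and blur the contrast it is meant to show. The imputation would also leave their counts alone, because stage 1 fills only what is classed as missing and stage 2 alters only what stage 1 imputed. The sensitivity analysis would then make the count outcomes look more complete than they are.

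**Working it through.** **1. The SAP's own threshold.** 48 weeks − 7 days = 48 − 1 = 47 weeks. This reproduces.

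**2. The rule as written.**

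| Participant | Planned (weeks) | Observed (weeks) | Under 47? | Exempt? | Flagged? |
|---|---|---|---|---|---|
| Full follow-up, leaves late | 48 | 46 | yes | no | yes |
| Truncated, completes | 44 | 44 | yes | yes | no (correct) |
| Truncated, withdraws early | 44 | 6 | yes | yes | no (38 of 44 planned weeks unobserved) |

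The second and third rows receive the same classification. The first, with 2 weeks unobserved, is the only one flagged.

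**3. The same logic applied to each truncated cohort.** Threshold = planned length − 1 week. July and August lengths are stated. The later ones follow from the four-week steps and the 24-week minimum.

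| Month of consent (2023) | Planned (weeks) | Threshold (weeks) | Unobserved if leaving at week 4 |
|---|---|---|---|
| July | 44 | 43 | 40 weeks (91%) |
| August | 40 | 39 | 36 weeks (90%) |
| September | 36 | 35 | 32 weeks (89%) |
| October | 32 | 31 | 28 weeks (88%) |
| November | 28 | 27 | 24 weeks (86%) |
| December | 24 | 23 | 20 weeks (83%) |

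A participant leaving at week 4 would be flagged in all six cohorts. Under the current text that person is flagged in none.

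**4. Size of the exempt cohort.** The documents do not report it. With even accrual of 238 participants over the stated 3 years, 238/36 = 6.61 per month, and × 6 months = 39.7, or about 40 (16.7% of 238). Protocol 10.2 states a target of 13 per month, which would give 13 × 6 = 78 (32.8%). That figure is doubtful as a recruitment rate: 469 eligible admissions/36 = 13.0 per month before the 50% uptake is applied, and with it 6.5 × 6 = 39. I take about 40 as the working value and 78 as an outer limit.

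**5. Early leavers within it.** No leaving rate is given. The only drop-out figure, 5% in the sample-size section, concerns people who never receive a first dose. As an assumption, 5% to 20% stopping early gives 2 to 8 of 40, or 4 to 16 of 78. These are ceilings on the number misclassified because they make no allowance for data recovered from records. The stage 2 shift would apply to fewer still, since it concerns only exits due to exacerbations or death.

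**The case against.** The strongest reply is that the authors meant only to spare follow-up that is short by design, and that a sensible programmer would read it so. That may be the intention, but the sentence has no condition about reaching the planned end. The trial statistician has access to allocations (Protocol 7.4), so the rule is better settled in writing than at programming.

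Several limits stand, and each rules out a stronger inference that a reader might draw:

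- *That truncated early leavers count as fully observed throughout.* They do not. The main count model in SAP 6.5.1.3 has log time on study as an offset, so six weeks count as six. That model assumes missing at random, however, which is the assumption the sensitivity analysis is meant to test.
- *That the whole sensitivity analysis drops them.* The 47-week rule governs only the two counts. Missing SGRQ values remain in scope.
- *That early deaths lose their imputation because of the exemption.* SAP 6.5.3 bars imputation past death for everyone, so the clear effect is on the descriptive comparison. The section also lists death among the stage 2 exits. That conflict affects all participants and is a separate matter.
- *That every early leaver's data are lost.* Protocol 7.11 follows participants lost to follow-up through hospital records to their planned end, and Protocol 7.8 seeks at least admissions and deaths after treatment stops. What remains is mainly consent withdrawals, plus moderate exacerbations. SAP 3.2.1 defines the latter as not hospitalised, so hospital records may miss them, and access to primary care records is optional (Protocol 7.2.1).
- *That a June 2023 enrolee is clearly on the other side of the line.* The footnotes in SAP 3.2.1 date truncation from June 2023, against July in SAP 2.1, so the edge of the exempt group is itself unsettled.

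**Conclusion.** The concern holds for the count outcomes in one sensitivity analysis. On its literal wording, SAP 6.5.3 classes truncated participants as non-missing whether or not they completed planned follow-up. Those who withdraw early therefore receive no count imputation at either stage. This is a stated rule that misclassifies people, and not simply a missing detail.

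The primary outcome, SGRQ and the main count analyses are not touched. The exempt cohort is about 40 of 238 if accrual was even. The number wrongly unflagged cannot be derived from the documents and depends on an assumed leaving rate and on how much the records recover. A reader might infer that the robustness check on the counts is invalid, but the documents do not support that: full-follow-up participants are handled as intended, and only early leavers in the last cohort are misplaced. The change is worth making before database lock because the planned end dates needed for a correct rule already exist.

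**What to change.** In SAP 6.5.3, replace the flat 47-week rule and its exemption with one rule for all: count data are missing when follow-up ends more than 7 days before the participant's own planned Final Follow-up, which is 48 weeks or the truncated length set by date of consent. For full-follow-up participants this still gives 47 weeks.

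The imputation end must change with it. Footnotes a and b should impute only to the planned end for truncated participants. Correcting the flag alone would have footnote a project their counts to 48 weeks, beyond what was ever planned.

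Two definitions should be settled at the same time. The June 2023 footnotes in SAP 3.2.1 should be reconciled with the July 2023 start in SAP 2.1. The planned date should be derived per participant and not from a month table alone, because SAP 2.1 gives the lengths as maxima and Protocol 8.4 carries dosing delays through to later visits. The SAP should say whether such delays move the planned date.

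The cost is a short SAP wording change and one derived variable from the consent date. No new data are needed.
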